[name]	Data Analyst	University of Alabama at Birmingham
[name]	Qualitative Interviewer	University of Alabama at Birmingham
TBD	Research Staff	University of North Carolina at Chapel Hill
[name]	Data Manager UNC	University of North Carolina at Chapel Hill
[name]	Project Manager	University of Pittsburgh

Statistical Analysis Plan

Study Design & Objectives. Our overall objective is to evaluate a novel theory-based PSM intervention, “Skills TO Manage Pain” (STOMP) developed for people with HIV (PWH). The design of the proposed study is a multicenter parallel-group individually randomized group clinical trial. The primary outcome is to evaluate the efficacy of STOMP, a theory-based intervention tailored to improving chronic pain in PWH immediately post intervention. The secondary outcomes are to investigate additional pain outcomes and proximal outcomes as potential mediators of STOMP’s impact on chronic pain immediately post intervention and at 3 months.

The study will be conducted at 2 institutions in the United States (University of Alabama at Birmingham (UAB) and University of North Carolina at Chapel Hill (UNC)), and we will enroll adult patients, ages >18 years of age, consented to participate in the CFAR Network of Integrated Clinical Systems (CNICS), English-speaking, having at least moderate chronic pain, ability and willingness to attend the group sessions at the date/time specified, and no plans for major surgery during the study period that would interfere with study procedures.

The primary hypothesis is STOMP will decrease pain severity and improve function (as measured by BPI-total) in PWH. To test this hypothesis, we propose a two-arm randomized trial of STOMP vs. an enhanced usual care comparison condition. Our primary outcome will be Brief Pain Inventory (BPI)-Total score and will be measured at baseline and immediately post-intervention (~12 weeks after first intervention session). Our secondary outcomes will be changes in additional pain scales (PEG and BPI subscales of BPI-pain severity and BPI-interference), pain self-efficacy questionnaire (PSEQ), Patient Health Questionnaire (PHQ-8), and pain catastrophizing scale (PCS) between groups immediately post intervention. We will examine sustained differences in primary and secondary outcomes at 3 months post intervention.

Sample Size Calculation. Our primary outcome is the BPI-Total score as described above. Given that 20 participants progress through the study at a time, our total sample size should be divisible by 20. A sample size of 210 will provide 85% power to detect a difference of 1 on a 10 point scale with at standard deviation of 2.4 assuming a two-sample t-test with equal variance. The IMMPACT guidelines suggest that a change of 1 on the BPI is a minimum clinically significant difference. Additionally, the difference we found in our pilot trial was 1 (SD=2.4). Therefore, a sample size of 210 is sufficient to detect this effect size. To become divisible by 20 and allow for 25% dropout (slightly more than in the pilot trial) we will recruit 280 participants. With our anticipated sample size, we will be able to estimate a margin-of-error of 1.5 percentage points for 95% intervals. For secondary outcomes, we can detect an effect size of 0.4, a medium effect, for continuous measures and a difference of proportions between 7.5% and 17% for binary measures, each with 85% power.

Interim & Final Analyses. We will not have any planned interim looks for stopping for efficacy, although safety and tolerability data will be monitored by the study DSMB at each meeting. The final analyses will be conducted once study follow-up is complete, after all data is

cleaned, and once the study database is locked. We anticipate database lock will happen by February 2024 with completion of primary analyses occurring by March of the same year.

Analysis Sets. The full analysis set will be based on an intention-to-treat (ITT) analysis with a per-protocol (PP) sensitivity analyses. The ITT analysis set will comprise all participants who have been randomized to either study arm, regardless of length of follow-up or actual intervention received.

Endpoint and Covariates

Our primary outcome will be the Brief Pain Inventory (BPI)-Total score, a commonly used composite measure of pain severity and the impact of pain on an individual's function. The BPI asks 11 questions about pain severity (pain at its worst, least, average, and right now) and the interference of pain in several aspects of patients' lives (activity, mood, walking ability, work, relations with other people, sleep, and enjoyment of life) on a scale of 0 (no pain/does not interfere) to 10 (pain as bad as you imagine/completely interferes). The BPI-Total score is the average score across all 11 questions.

There were no covariates included in our models, only time and treatment group indicator. We used linear mixed effects models which do not require adjustment for baseline as a fixed effect as it is included as an outcome. This allows for estimation of treatment effects at all follow-up times that takes into account any baseline differences between groups.

Handling of Missing Values. As a preventive measure, we will make every attempt to document all reasons for missing data. In addition, baseline characteristics will be compared between participants who do and do not withdraw from the study as a way to assess the impact of missing information and attrition. We will also compare the rates of lost-to-follow-up (LTF) between study arms.

Our general assumption will be that missing data is of the Missing at Random (MAR) mechanism. In this case, the use of linear mixed models for the primary analysis will be sufficient in reducing the impact that missing data has on biasing the primary results. Additionally, we will conduct a sensitivity analysis using multiple imputation via chained equations (MICE) to see how robust the overall inferences are.

Statistical Analyses.

The primary outcome – BPI-Total score – and the other secondary outcomes will be assessed as continuous variables. Linear mixed effects models will be performed to test differences between intervention and control conditions at the immediate post intervention and at 3 months. Models will include random effects for participant and therapy group. Therapy group is an identifier of the group of 20 that were randomized to create a STOMP group of 10. Fixed effects will be STOMP indicator, time and STOMP by time interaction. The primary hypothesis will be tested using the least squared means of each group at each time. We will check distributional

assumptions for these models using residual analysis including studentized residuals for individual observations, PRESS residuals which are composite residuals across an individual in longitudinal analysis, and Cook's distance. In compiling our analysis set, we will use an Intention to Treat (ITT) approach. We chose ITT for two reasons: 1) it fully exploits the benefits of balancing through randomization by including all patients who are randomized in the analysis; 2) it is a more "real-world" assessment of the intervention's impact as it allows for incomplete adherence and includes participants who may unintentionally cross over from the control to the intervention condition. Each of these issues can be handled well within the linear mixed models that will allow investigators to plot model-predicted trajectories for individuals with incomplete data. An additional advantage of linear mixed models is that they do not assume that the time between assessments is fixed and data for individuals who miss a time point can still be included. However, as this is the first efficacy trial to investigate STOMP, we will also conduct a per-protocol/as treated sensitivity analysis to understand the impact of the intervention without these complicating factors and adjust for differences by site. As a sensitivity analysis, missing data will be examined using multiple imputation methods. Specifically, multiple imputation using chained equations will be performed using previous baseline outcome data. Data will be imputed separately for each treatment group to improve efficiency and reduce bias in the treatment effect estimate.¹ Response to treatment defined by a reduction of at least 30% BPI Total score will be compared between groups using generalized linear mixed models with binary outcome using the same model effects and random components as the primary analysis.

Reference

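### The SAP's 1.5-percentage-point margin of error names no estimand and is not delivered at 210 or 280 participants; the 7.5%–17% binary range needs its N and base rates stated

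*Combined protocol and SAP*

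**What the plan says.** All the figures are in one paragraph of the SAP, Sample Size Calculation.

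- Primary outcome: "A sample size of 210 will provide 85% power to detect a difference of 1 on a 10 point scale", with "standard deviation of 2.4 assuming a two-sample t-test with equal variance".
- Recruitment: to reach a multiple of 20 and "allow for 25% dropout (slightly more than in the pilot trial) we will recruit 280 participants".
- Precision: "With our anticipated sample size", the SAP continues, "we will be able to estimate a margin-of-error of 1.5 percentage points for 95% intervals". No quantity, rate or N is attached.
- Secondary outcomes measured on scales: "For secondary outcomes, we can detect an effect size of 0.4, a medium effect, for continuous measures".
- Secondary outcomes that are yes or no: the same sentence gives the detectable range as "a difference of proportions between 7.5% and 17% for binary measures, each with 85% power". No N, alpha, test, base rate or direction is given.

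The secondary outcomes listed in SAP, Study Design & Objectives are all scales, and SAP, Statistical Analyses states that "the other secondary outcomes will be assessed as continuous variables". The plan does have binary outcomes elsewhere. The end of SAP, Statistical Analyses defines response as a reduction of at least 30% in BPI-Total, to be compared by a generalized linear mixed model. Protocol section II (Objectives) names retention in HIV care and virologic suppression. No expected rate is given for any of these.

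**The concern.** The 1.5-point figure is the only precision statement in the SAP. A margin in percentage points belongs to a proportion, whereas the primary outcome is a mean on a 0–10 scale. For proportions, a few hundred participants give 1.5 points only when the event is almost absent or almost universal, and the SAP mentions no such event.

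The binary range raises a related question. The paragraph works with two sample sizes, 210 evaluable and 280 recruited, and does not say which one the range uses. If the response rate is mid-range (an assumption, since none is stated) and about 210 outcomes are observed, the detectable difference is larger than the SAP says. A null response comparison could then be read as better powered than it was.

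**Working it through.** **Inputs.** 210 evaluable (105 per arm), 280 recruited (140 per arm), SD 2.4, difference 1, 85% power, 25% dropout (SAP, Sample Size Calculation); 1:1 allocation (protocol, Randomization). Alpha is not stated. Two-sided 0.05 is assumed; it matches the 95% intervals and reproduces the primary N. All figures are before any clustering by therapy group.

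**1. The primary calculation reproduces.** n per arm = 2(1.960 + 1.036)² × 2.4² / 1² = 103.4, so 104. With 105 per arm the t-test has 85.2% power, and 210 / 0.75 = 280.

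**2. The 1.5-point margin.** For one pooled proportion, half-width = 1.96 √(p(1−p)/N):

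| p | N=210 | N=280 |
|---|---|---|
| 5% | 2.9 | 2.6 |
| 10% | 4.1 | 3.5 |
| 50% | 6.8 | 5.9 |

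Setting the half-width to 0.015 and solving for p gives 1.25% (N=210, about 2.6 events) and 1.67% (N=280, about 4.7 events). Wald intervals are unreliable with so few events, and the alternatives are wider. With 3 events in 210, Wilson gives 1.81 points and Clopper–Pearson 1.91. With 5 events in 280, they give 1.67 and 1.77.

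Solving for N instead, N = 1.96² p(1−p) / 0.015² gives 811 at 5%, 1,537 at 10% and 4,269 at 50%.

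The planned analyses are between-arm contrasts, for which the half-width is larger:
- Difference of two proportions near 50%: 1.96 √(0.5/n) = 13.5 points (n=105) or 11.7 points (n=140).
- Difference in mean BPI-Total: 1.96 × 2.4 × √(2/105) = 0.65 scale points.

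None of these readings gives 1.5.

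**3. The 7.5%–17% range.** Pooled two-proportion test, with p̄ the mean of the two rates: power = Φ{[d√n − 1.96√(2p̄(1−p̄))] / √(p₁(1−p₁) + p₂(1−p₂))}. Setting power to 0.85 gives these detectable increases, in points, over an assumed range of control rates:

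| From | 105 per arm | 140 per arm |
|---|---|---|
| 1% | 9.6 | 7.6 |
| 10% | 15.7 | 13.3 |
| 20% | 18.7 | 16.0 |
| 30% | 20.1 | 17.3 |
| 40% | 20.5 | 17.8 |

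With 140 per arm the range nearly fits. It is 7.6 points from 1% and 17.05 from 27%, and it falls back to 16.9 from 57%. Between roughly 27% and 56% it exceeds 17, with a maximum of 17.8.

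With 105 per arm neither end holds generally:
- Low end, 0% vs 7.5%: (0.769 − 0.527) / 0.263 = 0.92, so power is 82%.
- High end, 41.5% vs 58.5%: (1.742 − 1.386) / 0.697 = 0.51, so power is 70%. With 140 per arm it is 81.5%.

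**4. The effect size of 0.4.** The two-sample t-test at 85% power detects 0.415 with 105 per arm and 0.359 with 140 per arm. The stated 0.4 is closer to 210, while the binary range in the same sentence is closer to 280.

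**The case against.** Four points can be made for the plan.

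- **280 is a natural reading.** The precision sentence directly follows the statement that 280 will be recruited, and SAP, Analysis Sets puts everyone randomized in the ITT set. The 7.5-point lower end also points to 280, because the pooled test does not reach it with 105 per arm. This stands for the binary range, which is therefore better described as missing its N and base rates than as miscalculated. However, membership of the ITT set does not supply outcomes for the 25% expected to drop out, and 280 does not rescue the 1.5-point margin.
- **The 0.4 may be a cautious rounding.** At 280 evaluable it has 91.5% power, so it does not prove that two sample sizes were mixed. That is conceded; it remains only suggestive.
- **The margin may concern a rare event.** It could, but then the event, its rate and N have to be stated, and none is.
- **Nothing depends on either sentence.** This is correct, and it limits the severity.

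A reader might go further and infer that the trial is underpowered, that the binary range is an arithmetic error, or that the plan has no binary outcome. The documents support none of these. The primary calculation reproduces, the range nearly reproduces at 280 evaluable, and the plan names a BPI-Total response as well as retention and virologic suppression.

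**Conclusion.** The margin-of-error figure is wrong as written. It has no estimand, and even on the most favourable reading the design delivers it only within about 1.25 points (210) or 1.67 points (280) of 0% or 100%. Near 50% the true half-width is about four times larger for one pooled proportion (5.9 to 6.8 points) and about eight to nine times larger for a between-arm difference (11.7 to 13.5 points).

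The binary range is a lesser, reporting problem. At 280 evaluable it falls short by at most 0.8 points (17.8 against 17). At the plan's 210 it falls short by up to about 3.5 points (20.5 against 17), and the 7.5-point end is not met under the pooled test.

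These results assume two-sided 0.05, the pooled normal approximation for two proportions, a range of base rates the documents do not give, and no clustering. Correlation of outcomes within STOMP groups would widen the figures. Severity is minor: the primary sample size, its power, trial conduct and every decision rule are unaffected.

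**What to change.** Two sentences in SAP, Sample Size Calculation.

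1. Delete the 1.5-point sentence, or replace it with the 95% half-width of a between-arm contrast for a named outcome and N. Examples at 105 per arm, before clustering: about ±0.65 points for mean BPI-Total, or about ±13.5 percentage points for a difference in response rates near 50%.
2. Restate the binary detectable differences with N, alpha, test, base rate and direction. With 105 per arm, two-sided 0.05, a pooled test and 85% power, these are about 16 points up from a 10% control rate, rising to about 20.5 points from 40%. If the present range was computed for 280 evaluable, say so. Tie it to the binary outcomes the plan names (30% BPI-Total response, retention, virologic suppression), and note that therapy-group clustering would widen the figures. State which N the 0.4 effect size uses.

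The cost is a text edit. The stated figures become less favourable; recruitment, primary power and conduct stay as they are.

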All participants in the intervention group will also receive a REDCAP assessment at baseline, post-intervention (0-month, after all sessions are completed), and then at 3, 6, 9 and 12 months post-intervention. The primary outcome will be at 3 months, and a 1-month window will be allowed after each timepoint for the patient to be contacted and assessed. An important medical event form will be administered to each participant at post-intervention (0-month) to screen for any unexpected medical incident, the severity of the event, its relation to the study, and medical follow-up. Viral load will also be

collected at baseline and at 12 months. At baseline, if a viral load from the prior 6 months is available in the medical record, that value will be recorded; otherwise, a viral load will be drawn. At 12 months, if a viral load in the prior 3 months is available in the medical record, that value will be recorded; otherwise, a viral load will be drawn. We will continue to conduct assessments every six months until the end of the study for all participants who complete the intervention by the beginning of Year 3. Participants who completed the baseline assessment by April 30, 2021 will continue to receive outcome assessments until April 2023 for a maximum of 41 months or 3 years. These assessments may be conducted by phone, if necessary, or in person. They will also participate in an audio-recorded in-person qualitative interview at the mid-point and end of the trial which will be transcribed using a third party company.

We will also investigate the intervention's impact on use of prescribed and non-prescribed opioids. Study staff will ask at each baseline and outcome assessment (0,3,6,9,12) the name of the participants' pharmacies along with the list of their current medications and dosage. Study staff will print out the medication lists and review it against the Opioid Medication Resource to identify the prescribed opioids. With written consent and a signed release of information from participants, a study staff member will contact the participants' pharmacy (or pharmacies) at the 12-month assessment to verify the self-reported information provided by the participants in the prior assessments. The data will be added into an excel spreadsheet for collection and analysis. Participants will receive up to 3 reminder calls at about a week and 48 hours prior to the next outcome assessment.

Qualitative interviews

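### The primary model carries baseline BPI-Total only as an unconstrained outcome and omits both randomisation strata, so the contrast its wording points to does not take baseline differences into account

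*Combined protocol and SAP*

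**What the plan says.** The SAP section Endpoint and Covariates says: "There were no covariates included in our models, only time and treatment group indicator". It explains that baseline needs no adjustment because it is itself an outcome in the mixed model, and adds: "This allows for estimation of treatment effects at all follow-up times that takes into account any baseline differences between groups".

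The SAP section Statistical Analyses gives the model: "Fixed effects will be STOMP indicator, time and STOMP by time interaction", with random effects for participant and therapy group. It says the models test "differences between intervention and control conditions at the immediate post intervention and at 3 months", and "The primary hypothesis will be tested using the least squared means of each group at each time". No contrast is written out.

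On the time point, SAP Study Design & Objectives says that BPI-Total "will be measured at baseline and immediately post-intervention". The protocol's Assessments text under III.d says "The primary outcome will be at 3 months".

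The protocol's Randomization section stratifies by long-term opioid therapy and by chronic multisite pain. Neither factor appears in the primary model. Site adjustment is mentioned only alongside the per-protocol/as-treated sensitivity analysis.

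**The concern.** A longitudinal model with baseline among the outcomes can use baseline information well, but only if the arms share a baseline mean or if the contrast is a change from baseline. Here the STOMP main effect gives each arm its own baseline mean, and the test wording describes arm means compared at a follow-up visit. That combination makes no use of the arm-level baseline difference, yet the SAP tells its reader that it does.

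At stake is precision on the primary endpoint. So is exposure of the primary estimate to a chance difference in baseline pain that the trial will already have measured. The missing strata are a smaller matter of the same kind: the analysis does not reflect how participants were randomised.

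**Working it through.** **Inputs from the documents.** Difference 1 point, SD 2.4, two-sample t-test, 210 analysable, 85% power, 25% dropout, 280 recruited (SAP, Sample Size Calculation); 1:1 allocation (protocol, Randomization).

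**Assumed.** Two-sided 5%; equal SDs at baseline and follow-up; baseline-to-follow-up correlation ρ = 0.3, 0.5 or 0.7; no therapy-group clustering. The SAP does not say whether 2.4 is the SD of the score or of the change, so both are shown.

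**1. The plan's own figure.** With 105 per arm, SE = 2.4 × √(2/105) = 0.331, and noncentral-t power is 85.2%. 210/(1 − 0.25) = 280. Both reproduce.

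**2. What the planned contrast estimates.** With arm, time and arm-by-time all free, there is one mean per arm per visit. With complete data the fitted means are the raw means. In simulation of this model (participant random intercept only, 140 per arm, ρ = 0.6) the post-intervention least-squares mean difference matched the raw difference to about 1e-13. With 25% of participants lacking follow-up, the model borrows from the dropouts' baselines and the two no longer coincide. The estimate still moves with the arm-level baseline difference: expected slope ρ = 0.6, simulated 0.52 over 60 runs.

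**3. Variance relative to the raw follow-up difference (equal SDs).**
- Raw follow-up: 1
- Change from baseline: 2(1 − ρ)
- Baseline-adjusted or common-baseline: 1 − ρ²

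The ratio of adjusted to change variance is (1 − ρ²)/[2(1 − ρ)] = (1 + ρ)/2, which never exceeds 1. In large samples adjustment is therefore never less precise than change, and 1 − ρ² never exceeds 1, so it is never less precise than raw.

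**4. Power at 105 per arm, true difference 1.** If 2.4 is the score SD, the SDs are 2.4 (raw), 2.4√(2(1 − ρ)) (change) and 2.4√(1 − ρ²) (adjusted). If 2.4 is the SD of change, the score SD is 2.4/√(2(1 − ρ)) = 2.03/2.40/3.10 and the adjusted SD is 2.4√((1 + ρ)/2) = 1.93/2.08/2.21.

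| Meaning of 2.4 | Contrast | ρ = 0.3 | ρ = 0.5 | ρ = 0.7 |
|---|---|---|---|---|
| SD of score | Raw follow-up | 85.2% | 85.2% | 85.2% |
| | Change | 71.9% | 85.2% | 97.3% |
| | Baseline-adjusted | 88.3% | 93.4% | 98.8% |
| SD of change | Raw follow-up | 94.5% | 85.2% | 64.3% |
| | Change | 85.2% | 85.2% | 85.2% |
| | Baseline-adjusted | 96.1% | 93.4% | 90.3% |

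**5. All 280 randomised, 35 per arm with no follow-up, 2.4 as score SD.** Generalised least squares on three visits, power = Φ(1/SE − 1.96). SEs at ρ = 0.3/0.5/0.7:
- Post-intervention contrast: 0.327/0.321/0.310, power 86.3/87.7/89.7%
- Change contrast: 0.374/0.321/0.252, power 76.1/87.7/97.8%
- Common-baseline model: 0.316/0.287/0.237, power 88.6/93.7/98.8%

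So the mixed model's use of dropouts' baselines recovers only part of the gain.

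**6. Chance imbalance.** With 140 per arm and SD 2.4, the SE of the baseline difference is 2.4 × √(2/140) = 0.29 points. At ρ = 0.5, a one-SE imbalance moves the raw estimate by 0.5 × 0.29 = 0.14 points and the change estimate by 0.14 the other way, against a target of 1.

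**7. Strata.** Suppose the strata explain 5% or 15% of the variance (assumed) and the arms balance within them. Type I error of the post-score test without them is 2[1 − Φ(1.96/√(1 − R²))] = 4.4% or 3.4%. Added to baseline adjustment at ρ = 0.5, they raise power from 93.4% to 93.8% or 94.7%. With complete data, time-constant strata effects cancel from a change contrast.

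**The case against.** The strongest reply is that this is a preference for efficiency. An arm-by-time mixed model with baseline as an outcome is a recognised and valid analysis. The sample size was set for an unadjusted two-sample comparison, and that comparison has the power it was set for if 2.4 is the score SD. This stands: it makes the point one of precision and accurate description. It does not rescue the sentence about baseline differences.

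A second reply is that a change-from-baseline contrast is meant, which would make that sentence true. Some wording leans that way ("Our secondary outcomes will be changes in additional pain scales"), but it concerns secondary outcomes; the other instances are a guideline threshold in the sample-size section and the responder definition. None describes the primary test, and change would still be no more precise than adjustment.

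Four stronger readings are tempting, and the documents do not support them:
- **That the primary contrast is wholly open.** SAP Study Design & Objectives and Statistical Analyses together point to the arm difference at immediate post-intervention. What is missing is the explicit statement.
- **That the primary test is biased or its type I error inflated.** Randomisation keeps both contrasts unbiased on average, and leaving out the strata makes the post-score test, if anything, slightly conservative.
- **That 210/280 is wrong.** It reproduces.
- **That the table gives the trial's actual power.** It ignores clustering. Only STOMP participants attend group sessions, and they do so after baseline, so clustering from that source would lower the absolute figures. The table is for comparing contrasts.

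**Conclusion.** The concern holds as one of precision and accuracy. The contrast the SAP's wording points to does not take arm-level baseline differences into account, contrary to the SAP's own statement, and both stratification factors are left out. That much follows from the text with high confidence.

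The size is less certain, because the documents give neither the correlation nor the meaning of 2.4. Across the assumed range, baseline adjustment adds from 1.6 points of power (94.5% to 96.1%) to 26.0 points (64.3% to 90.3%) over the raw contrast; at ρ = 0.5 it adds 8.2 points (85.2% to 93.4%) on either reading of the SD. It was at least as powerful as both alternatives in every case computed. The strata contribute little beyond matching the analysis to the randomisation. The change should be made, but the trial's validity does not depend on it.

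**What to change.** 1. Reconcile the primary time point between the protocol (3 months) and the SAP (immediately post-intervention). This is a separate defect, but the contrast cannot be written until it is settled.
2. Write the primary contrast explicitly. If the SAP's time point stands, it is the arm difference in mean BPI-Total at immediate post-intervention.
3. Estimate it with a constrained longitudinal model (common baseline mean, no arm effect at baseline), or with baseline BPI-Total as a covariate and only follow-up visits as outcomes.
4. Secondarily, add fixed effects for long-term opioid therapy and chronic multisite pain.
5. Replace the sentence about baseline differences with one that is true of the model used.

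The cost is SAP wording and at most three degrees of freedom: two for the strata and one if baseline is a covariate (none for baseline under the common-baseline model). Baseline BPI-Total and both stratification factors are already part of the trial's data.

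Timing matters. The covariate paragraph is written in the past tense, and the SAP anticipates database lock by February 2024. The change should be made before unblinding. If the analysis has already been run, keep the specified model as primary and report the adjusted model as a labelled sensitivity analysis.
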